16. ETHICS

The clinical trial will be performed in accordance with the guidelines set by the World Medical Assembly ([Declaration of Helsinki](#), last amendment in Fortaleza, Brazil, October 2013). Prior written approval of the study protocol and of the informed consent form will be obtained from the appropriate local Medical Ethics Review Board.

16.1. Study-Specific Design Considerations

Potential subjects will be fully informed of the risks and requirements of the study and during the study subjects will be given any new information that may affect their decision to continue participation. They will be told that their consent to participate in the study is voluntary and may be withdrawn at any time with no reason given and without penalty or loss of benefits to which they would otherwise be entitled. Only subjects who are fully able to understand the risks, benefits, and potential AEs of the study, and provide their consent voluntarily will be enrolled.

16.2. Investigator Responsibilities

The Investigator is responsible for ensuring that the clinical study is performed in accordance with the protocol, current International Conference on Harmonization (ICH) guidelines on Good Clinical Practice (GCP), and applicable regulatory and country specific requirements.

Good Clinical Practice is an international ethical and scientific quality standard for designing, conducting, recording, and reporting studies that involve the participation of human subjects. Compliance with this standard provides public assurance that the rights, safety, and wellbeing of study subjects are protected, consistent with the principles that originated in the [Declaration of Helsinki](#), and that the clinical study data are credible.

16.3. Institutional Review Board (IRB)

Before the start of the study, the Investigator (or Sponsor where required) will provide the IRB with current and complete copies of the following documents:

- Final protocol and, if applicable, amendments
- Sponsor-approved ICF (and any other written materials to be provided to the subjects)
- Investigator's Brochure (or equivalent information) and addenda
- Sponsor-approved subject recruiting materials
- Information on compensation for study-related injuries or payment to subjects for participation in the study, if applicable
- Investigator's curriculum vitae or equivalent information (unless not required, as documented by IRB)
- Information regarding funding, name of the Sponsor, institutional affiliations, other potential conflicts of interest, and incentives for subjects
- Any other documents that the IRB requests to fulfill its obligation

This study will be undertaken only after the IRB has given full approval of the final protocol, amendments (if any), the ICF, applicable recruiting materials, and subject compensation programs, and the Sponsor has received a copy of this approval. This approval letter must be dated and must clearly identify the IRB and the documents being approved.

During the study, the Investigator (or Sponsor where required) will send the following documents and updates to the IRB for their review and approval, where appropriate:

- Protocol amendments
- Revision(s) to ICF and any other written materials to be provided to subjects
- If applicable, new or revised subject recruiting materials approved by the Sponsor
- Revisions to compensation for study-related injuries or payment to subjects for participation in the study, if applicable
- Investigator's Brochure addenda or new edition(s)
- Summaries of the status of the study at intervals stipulated in guidelines of the IRB (at least annually)
- Reports of AEs that are serious, unlisted, and associated with the investigational drug
- New information that may adversely affect the safety of the subjects or the conduct of the study
- Deviations from or changes to the protocol to eliminate immediate hazards to the subjects
- Report of deaths of subjects under the Investigator's care
- Notification if a new Investigator is responsible for the study at the site

- Annual IND Update Report, Short Term Study Specific Safety Summary and Line Listings, where applicable
- Any other requirements of the IRB

For all protocol amendments (excluding the ones that are purely administrative, with no consequences for subjects, data or study conduct), the amendment and applicable informed consent form and assent form revisions must be submitted promptly to the IRB for review and approval before implementation of the change(s), except when necessary to eliminate immediate hazard to the study subjects. If a deviation from, or a change to the protocol was implemented to eliminate an immediate hazard to study subjects, then the implemented deviation or change, the reasons for it, and, if appropriate, the protocol amendment should be submitted to the IRB as soon as possible.

The re-approval of the clinical study by the IRB should be documented in writing.

At the end of the study, the Investigator (or Sponsor where required) will notify the IRB about the study completion.

16.4. Privacy of Personal Data

The collection and processing of personal data from subjects enrolled in this study will be limited to those data that are necessary to investigate the safety, quality, and utility of the investigational study drug(s) used in this study.

These data must be collected and processed with adequate precautions to ensure confidentiality and compliance with applicable data privacy protection laws and regulations. Appropriate technical and organizational measures to protect the personal data against unauthorized disclosures or access, accidental or unlawful destruction, or accidental loss or alteration must be put in place. Sponsor personnel whose responsibilities require access to personal data agree to keep the identity of study subjects confidential.

The informed consent obtained from the subject includes explicit consent for the processing of personal data and for the Investigator to allow direct access to his or her original medical records for study-related monitoring, audit, IRB review, and regulatory inspection. This consent also addresses the transfer of the data to other entities and to other countries.

17. DATA CONFIDENTIALITY, DISCLOSURE OF DATA, AND PUBLICATION

Data generated for the study should be stored by the Investigator in a limited-access file area and be accessible only to representatives of the study site, Romark, the IRB, and FDA/relevant regulatory agencies. Medical information resulting from a subject's participation in this study may be given to the subject's personal physician or to the appropriate medical personnel responsible for the subject's welfare.

No information that can be related to a specific individual subject may be released or used in any fashion without the signed written consent of that subject. All reports and communications relating to study subjects will identify subjects only by initials and subject identification number. The Investigator will keep complete subject identification for

purposes of long-term follow-up, if needed. This information will be treated with strict adherence to professional standards of confidentiality.

Site personnel will enter data relating to each subject's participation in the study into the EDC system provided by the Sponsor. In the EDC system, identification numbers and initials will be used to identify subjects. Subject names will not be used in the CRFs. Management of data from the EDC system and the production of the clinical study report will be the responsibility of the Sponsor. Access to the database will be restricted to employees who have been trained to use the system. Access to the EDC system and study report will be limited to the IRB, FDA or other regulatory agencies and the Sponsor.

Presentation and/or publication of the results of the study is encouraged provided that The Romark Institute for Medical Research is notified in advance of the author's intent and is given the opportunity to review the manuscript or abstract 45 days prior to its submission for presentation at a scientific meeting or for publication in a scientific journal. The Investigators will have complete autonomy regarding the content and wording of any abstracts, presentations, and scientific publications arising from this study, including the decision of whether or not to publish.

18. DATA AND REPORT REQUIREMENTS

Data required by The Romark Institute for Medical Research prior to approval and initiation of the study are as follows:

1. Curriculum vitae of the Principal Investigator and all Co-Investigators.
2. Copy of the IRB-approved Informed Consent and subject information forms.
3. Copy of the IRB approval for the conduct of the study.

Data and materials required by The Romark Institute for Medical Research before the study can be considered complete and terminated are as follows:

1. Pre- and post-treatment history, physical examination and subject evaluations.
2. Pre- as well as interim and post-treatment laboratory findings and all special test results.
3. EDC forms properly completed and signed by the Principal Investigator.
4. Drug Inventory Logs indicating drug dispensed and return of the unused supplies to the Sponsor or destruction by study site.
5. Signed Informed Consent/Accent from each subject.

21. APPENDICES

- Appendix I: Study Schedule
- Appendix II: Toxicity Grading for Adverse Events
- Appendix III: List of Essential Documents for the Investigative Site
- Appendix IV: Protocol Revision History
- Appendix V: Declaration of Helsinki

21.1. Appendix I: Study Schedule

Table 9: Schedule of Assessments

	Screening (Day-90 to Day 1)	Baseline (Day 1)	Day 1- Week 6	Weeks 1, 3, 6	Week 8	Suspected ARI Visit	Unsched- uled Visit
Signed informed consent	X						
Complete medical history	X						
Physical examination	X			X ¹	X	X ¹	X
Body weight/vital signs ²	X			X		X	X
Demographics/smoking history	X						
Record body temperature	X			X		X	X
Evaluate according to inclusion/exclusion criteria	X						
Collect nasopharyngeal swabs		X				X ³	X
Blood sample for pharmacokinetics ⁴				X			
Blood sample for laboratory safety tests ⁵	X			X			X
Blood sample for antibody testing	X			X ⁷	X		
Urine sample for routine urinalysis ⁵	X			X			X
Record concomitant medications		X	X	X	X	X	X
Randomization/dispense study medication		X					
Complete symptom diary		X	X ⁶			X	
First dose, then study medication twice daily for 6 weeks		X	X				
Instructions re: dosing, concomitant medications, follow-up visits and seeking emergency care		X		X			X
Review/record adverse events		X		X	X	X	X
Inquire regarding cold/flu symptoms and refer for Suspected ARI visit if yes			X				
Review compliance with study medication, collect container with unused medication, complete pill count log form				X			
Document any infections diagnosed during follow-up period					X		

¹ Physical examination as warranted by the Investigator for any change from Baseline.

² Body weight and collection of vital signs to include blood pressure, pulse, respiratory rate and body temperature.

³ Nasopharyngeal swabs are to be collected at a Suspected ARI Visit and repeat swabs collected 24 to 36 hours and 4 to 5 days later.

⁴ Week 3 and 6 visit only, blood sample to be collected pre-dose.

⁵ Week 3 and 6 visit only, laboratory safety tests include hemoglobin, hematocrit, complete blood count (total and differential), platelet count, random blood sugar, total cholesterol, HDL, LDL, triglycerides, albumin, AST, ALT, GGT, alkaline phosphatase, bilirubin (total/direct), BUN, creatinine, sodium, potassium, chloride and routine urinalysis (appearance, glucose, proteins and blood).

⁶ If the subject meets the criteria for a Suspected ARI, then he/she will be asked to complete a symptom diary, and then continue daily with the symptom diary between 4 pm and 8 pm each day until the subject returns to usual health for 3 consecutive days or until the Week 6 Visit, whichever comes first. A caregiver may assist the subject with the diary entry if needed.

⁷ Week 6 only.

21.2. Appendix II: Toxicity Grading for Adverse Events

[Derived and adapted from “Guidance for Industry: Toxicity Grading Scale for Healthy Adult and Adolescent Volunteers Enrolled in Preventive Vaccine Clinical Trials”, US Dept. of HHS, FDA, CDER, September 2007]

Table 10: Table for Clinical Abnormalities: Vital Signs

Vital Signs*	Mild (Grade 1)	Moderate (Grade 2)	Severe (Grade 3)	Potentially Life Threatening (Grade 4)
Fever (°C)** (°F)**	38.0 – 38.4 100.4 – 101.1	38.5 – 38.9 101.2 – 102.0	39.0 – 40 102.1 – 104	> 40 > 104
Tachycardia – beats per minute	101 – 115	116 – 130	> 130	ER visit or hospitalization for arrhythmia
Bradycardia – beats per minute***	50 – 54	45 – 49	< 45	ER visit or hospitalization for arrhythmia
Hypertension (systolic) – mm Hg	141 – 150	151 – 155	> 155	ER visit or hospitalization for malignant hypertension
Hypertension (diastolic) – mm Hg	91 – 95	96 – 100	> 100	ER visit or hospitalization for malignant hypertension
Hypotension (systolic) – mm Hg	85 – 89	80 – 84	< 80	ER visit or hospitalization for hypotensive shock
Respiratory Rate – breaths per minute	17 – 20	21 – 25	> 25	Intubation

* Subject should be at rest for all vital sign measurements.

** Oral temperature; no recent hot or cold beverages or smoking.

*** When resting heart rate is between 60 – 100 beats per minute. Use clinical judgment when characterizing bradycardia among some healthy subject populations, for example, conditioned athletes.

Table 11: Table for Clinical Abnormalities: Systemic (General)

Systemic (General)	Mild (Grade 1)	Moderate (Grade 2)	Severe (Grade 3)	Potentially Life Threatening (Grade 4)
Nausea/vomiting	No interference with activity or 1-2 episodes/24 hours	Some interference with activity or > 2 episodes/24 hours	Prevents daily activity, requires outpatient IV hydration	ER visit or hospitalization for hypotensive shock
Diarrhea	2-3 loose stools or <400 gms/24 hours	4-5 stools or 400-800 gms/24 hours	6 or more watery stools or >800 gms/24 hours or requires outpatient IV hydration	ER visit or hospitalization
Headache	No interference with activity	Repeated use of non-narcotic pain reliever >24 hours or some interference with activity	Significant; any use of narcotic pain reliever or prevents daily activity	ER visit or hospitalization
Fatigue	No interference with activity	Some interference with activity	Significant; prevents daily activity	ER visit or hospitalization
Myalgia	No interference with activity	Some interference with activity	Significant; prevents daily activity	ER visit or hospitalization

Table 12: Table for Clinical Abnormalities: Systemic Illness

Systemic Illness	Mild (Grade 1)	Moderate (Grade 2)	Severe (Grade 3)	Potentially Life Threatening (Grade 4)
Illness or clinical adverse event (as defined according to applicable regulations)	No interference with activity	Some interference with activity not requiring medical intervention	Prevents daily activity and requires medical intervention	ER visit or hospitalization

The laboratory values provided in the tables below serve as guidelines and are dependent upon institutional normal parameters.

Table 13: Table for Laboratory Abnormalities: Serum

Serum*	Mild (Grade 1)	Moderate (Grade 2)	Severe (Grade 3)	Potentially Life Threatening (Grade 4)**
Sodium – Hyponatremia mEq/L	132 – 134	130 – 131	125 – 129	< 125
Sodium – Hypernatremia mEq/L	144 – 145	146 – 147	148 – 150	> 150
Potassium – Hyperkalemia mEq/L	5.1 – 5.2	5.3 – 5.4	5.5 – 5.6	> 5.6
Potassium – Hypokalemia mEq/L	3.5 – 3.6	3.3 – 3.4	3.1 – 3.2	< 3.1
Chloride – mEq/L**	Asymptomatic or mild symptoms; clinical or diagnostic observations only; intervention not indicated	Moderate; minimal, local or noninvasive intervention indicated; limiting age-appropriate instrumental ADL	Severe or medically significant but not immediately life threatening; hospitalization or prolongation of existing hospitalization indicated; disabling; limiting self care ADL	Life-threatening consequences; urgent intervention indicated
Glucose – Hypoglycemia mg/dL	65 – 69	55 – 64	45 – 54	< 45
Glucose – Hyperglycemia Fasting – mg/dL Random – mg/dL	100 – 110 110 – 125	111 – 125 126 – 200	>125 >200	Insulin requirements or hyperosmolar coma
Blood Urea Nitrogen BUN mg/dL	23 – 26	27 – 31	> 31	Requires dialysis
Creatinine – mg/dL	1.5 – 1.7	1.8 – 2.0	2.1 – 2.5	> 2.5 or requires dialysis

Serum*	Mild (Grade 1)	Moderate (Grade 2)	Severe (Grade 3)	Potentially Life Threatening (Grade 4)**
Calcium – hypocalcemia mg/dL	8.0 – 8.4	7.5 – 7.9	7.0 – 7.4	< 7.0
Calcium – hypercalcemia mg/dL	10.5 – 11.0	11.1 – 11.5	11.6 – 12.0	> 12.0
Magnesium – hypomagnesemia mg/dL	1.3 – 1.5	1.1 – 1.2	0.9 – 1.0	< 0.9
Phosphorous – hypophosphatemia mg/dL	2.3 – 2.5	2.0 – 2.2	1.6 – 1.9	< 1.6
CPK – mg/dL	1.25 – 1.5 x ULN	1.6 – 3.0 x ULN	3.1 – 10 x ULN	> 10 x ULN
Albumin – Hypoalbuminemia g/dL	2.8 – 3.1	2.5 – 2.7	< 2.5	--
Total Protein – Hypoproteinemia g/dL	5.5 – 6.0	5.0 – 5.4	< 5.0	--
Alkaline phosphate – increase by factor	1.1 – 2.0 x ULN	2.1 – 3.0 x ULN	3.1 – 10 x ULN	> 10 x ULN
Liver Function Tests – ALT, AST increase by factor	1.1 – 2.5 x ULN	2.6 – 5.0 x ULN	5.1 – 10 x ULN	> 10 x ULN
Liver Function Tests – GGT** increase by factor	>ULN – 2.5 x ULN	>2.5 – 5.0 x ULN	>5.0 – 20.0 x ULN	>20.0 x ULN
Bilirubin – when accompanied by any increase in Liver Function Test increase by factor	1.1 – 1.25 x ULN	1.26 – 1.5 x ULN	1.51 – 1.75 x ULN	> 1.75 x ULN
Bilirubin – when Liver Function Test is normal; increase by factor	1.1 – 1.5 x ULN	1.6 – 2.0 x ULN	2.0 – 3.0 x ULN	> 3.0 x ULN
Cholesterol**	ULN – 300 mg/dL	>300 – 400 mg/dL	>400 – 500 mg/dL	>500 mg/dL

Serum*	Mild (Grade 1)	Moderate (Grade 2)	Severe (Grade 3)	Potentially Life Threatening (Grade 4)**
Triglycerides – mg/dL**	150 mg/dL – 300 mg/dL	>300 mg/dL – 500 mg/dL	>500 mg/dL - 1000 mg/dL	>1000 mg/dL
HDL – mg/dL**	Asymptomatic or mild symptoms; clinical or diagnostic observations only; intervention not indicated	Moderate; minimal, local or noninvasive intervention indicated; limiting age-appropriate instrumental ADL	Severe or medically significant but not immediately life threatening; hospitalization or prolongation of existing hospitalization indicated; disabling; limiting self care ADL	Life-threatening consequences; urgent intervention indicated
LDL – mg/dL**	Asymptomatic or mild symptoms; clinical or diagnostic observations only; intervention not indicated	Moderate; minimal, local or noninvasive intervention indicated; limiting age-appropriate instrumental ADL	Severe or medically significant but not immediately life threatening; hospitalization or prolongation of existing hospitalization indicated; disabling; limiting self care ADL	Life-threatening consequences; urgent intervention indicated

* The laboratory values provided in the tables serve as guidelines and are dependent upon institutional normal parameters. Institutional normal reference ranges should be provided to demonstrate that they are appropriate.

** Derived from the National Institutes of Health, National Cancer Institute Common Terminology Criteria for Adverse Events (CTCAE) Version 5.0. ADL- Activities of Daily Living refer to preparing meals, shopping for groceries or clothes, using the telephone, managing money, etc. selfcare ADL refer to bathing, dressing and undressing, feeding self, using the toilet, taking medications, and not bedridden.

Note: "ULN" is the upper limit of the normal range.

Table 14: Table for Laboratory Abnormalities: Hematology

Hematology*	Mild (Grade 1)	Moderate (Grade 2)	Severe (Grade 3)	Potentially Life Threatening (Grade 4)
Hemoglobin (Female) – gm/dL	11.0 – 12.0	9.5 – 10.9	8.0 – 9.4	< 8.0
Hemoglobin (Female) change from baseline value – gm/dL	Any decrease – 1.5	1.6 – 2.0	2.1 – 5.0	> 5.0
Hemoglobin (Male) – gm/dL	12.5 – 13.5	10.5 – 12.4	8.5 – 10.4	< 8.5
Hemoglobin (Male) change from baseline value – gm/dL	Any decrease – 1.5	1.6 – 2.0	2.1 – 5.0	> 5.0
Hematocrit - %**	Asymptomatic or mild symptoms; clinical or diagnostic observations only; intervention not indicated	Moderate; minimal, local or noninvasive intervention indicated; limiting age-appropriate instrumental ADL	Severe or medically significant but not immediately life threatening; hospitalization or prolongation of existing hospitalization indicated; disabling; limiting self care ADL	Life-threatening consequences; urgent intervention indicated
WBC Increase - cell/mm ³	10,800 – 15,000	15,001 – 20,000	20,001 – 25,000	> 25,000
WBC Decrease - cell/mm ³	2,500 – 3,500	1,500 – 2,499	1,000 – 1,499	< 1,000
Lymphocytes Decrease - cell/mm ³	750 – 1,000	500 – 749	250 – 499	< 250
Neutrophils Decrease - cell/mm ³	1,500 – 2,000	1,000 – 1,499	500 – 999	< 500
Eosinophils - cell/mm ³	650 – 1500	1501 - 5000	> 5000	Hypereosinophilic
Platelets Decreased - cell/mm ³	125,000 – 140,000	100,000 – 124,000	25,000 – 99,000	< 25,000

Hematology*	Mild (Grade 1)	Moderate (Grade 2)	Severe (Grade 3)	Potentially Life Threatening (Grade 4)
PT – increase by factor (prothrombin time)	1.0 – 1.10 x ULN	1.11 – 1.20 x ULN	1.21 – 1.25 x ULN	> 1.25 ULN
PTT – increase by factor (partial thromboplastin time)	1.0 – 1.2 x ULN	1.21 – 1.4 x ULN	1.41 – 1.5 x ULN	> 1.5 x ULN
Fibrinogen increase - mg/dL	400 – 500	501 – 600	> 600	--
Fibrinogen decrease - mg/dL	150 – 200	125 – 149	100 – 124	< 100 or associated with gross bleeding or disseminated intravascular coagulation (DIC)

* The laboratory values provided in the tables serve as guidelines and are dependent upon institutional normal parameters. Institutional normal reference ranges should be provided to demonstrate that they are appropriate.

** Derived from the National Institutes of Health, National Cancer Institute Common Terminology Criteria for Adverse Events (CTCAE) Version 5.0. ADL- Activities of Daily Living refer to preparing meals, shopping for groceries or clothes, using the telephone, managing money, etc. selfcare ADL refer to bathing, dressing and undressing, feeding self, using the toilet, taking medications, and not bedridden.

Note: "ULN" is the upper limit of the normal range.

Table 15: Table for Laboratory Abnormalities: Urine

Urine*	Mild (Grade 1)	Moderate (Grade 2)	Severe (Grade 3)	Potentially Life Threatening (Grade 4)
Protein	Trace	1+	2+	Hospitalization or dialysis
Glucose	Trace	1+	2+	Hospitalization for hyperglycemia
Blood (microscopic) – red blood cells per high power field (rbc/hpf)	1 – 10	11 – 50	> 50 and/or gross blood	Hospitalization or packed red blood cells (PRBC) transfusion

* The laboratory values provided in the tables serve as guidelines and are dependent upon institutional normal parameters. Institutional normal reference ranges should be provided to demonstrate that they are appropriate.

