#### **Urinalysis:**

Appearance, glucose, protein, and blood.

Clinical laboratory results and the change from baseline (CFB, baseline defined as the value at the baseline visit) will be summarized for the safety population with summary statistics (mean, standard deviation, n, minimum, median, maximum) by time point for each treatment group. Clinical laboratory results will be classified as "Normal", or "Abnormal"; "Abnormal" results will be further classified by the PI as "Clinically significant" (CS) or "Not clinically significant" (NCS). Clinical laboratory results will be summarized by a shift table from baseline with categories "Normal", "Abnormal (NCS)", and "Abnormal (CS)". Urinalysis appearance results will appear only in the shift table.

All clinically significant abnormal laboratory findings will be reported as AEs. All AEs recorded will be listed.

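### The SAP's laboratory shift tables cannot show worsening within a category or low/high direction, so results judged not clinically significant get no graded or directional comparison by arm

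*Protocol*

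**What the plan says.** SAP 5.2, Laboratory Tests, classes each result as normal or abnormal. Abnormal "results will be further classified by the PI as" clinically significant (CS) or not clinically significant (NCS). The section then states: "Clinical laboratory results will be summarized by a shift table from baseline with categories" Normal, Abnormal (NCS) and Abnormal (CS). No high/low split, grade or numeric cut-off enters. The text does not say whether the shift is to each visit or to the worst post-baseline value. The table list in SAP 8.0 has shift tables 14.3.2.2 (hematology), 14.3.3.2 (chemistry) and 14.3.4.2 (urinalysis), and no laboratory table by grade or direction.

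The same section plans other laboratory output: mean, SD, n, minimum, median and maximum of values and change from baseline, by time point and arm. All CS abnormalities are to be reported as adverse events, and SAP 5.2 tabulates adverse events by preferred term and severity grade (Table 14.3.1.3). Listings 16.2.8.1 to 16.2.8.3 hold the individual values.

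Protocol Appendix II, Tables 13 to 15, grades laboratory abnormalities from 1 to 4. Among the tests collected (Protocol 5.9), four have rows in both directions: sodium ("Sodium – Hyponatremia mEq/L" and its hypernatremia counterpart), potassium ("Potassium – Hyperkalemia mEq/L" and "Potassium – Hypokalemia mEq/L"), glucose ("Glucose – Hypoglycemia mg/dL" and its hyperglycemia counterpart) and white cells. Others, such as "Liver Function Tests – ALT, AST increase by factor", run in one direction.

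**The concern.** A shift table is the usual place to see how many subjects per arm got worse on a laboratory test. Here a subject whose value is abnormal at baseline and deteriorates moves to another cell only if the investigator's label changes. A subject who goes from below to above the normal range can stay in the same cell. If many residents start with abnormal values, which is an assumption because the documents give no rate, a good part of the data sits where the table has least resolution.

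What is at stake is detection of a treatment-related laboratory effect. Protocol 1.2.3 describes 89 subjects aged 65 or over exposed to this tablet: 14 with a single dose and 75 treated for 5 days. This trial doses for 6 weeks, so its between-arm laboratory summaries carry weight.

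**Working it through.** The plan states no figure to reproduce. The check asks which baseline-to-post-baseline transitions the SAP's categories can separate, compared with Appendix II grades.

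**Inputs.** Potassium limits in mEq/L, from Appendix II Table 13:

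| Direction | Grade 1 | Grade 2 | Grade 3 | Grade 4 |
|---|---|---|---|---|
| High | 5.1–5.2 | 5.3–5.4 | 5.5–5.6 | > 5.6 |
| Low | 3.5–3.6 | 3.3–3.4 | 3.1–3.2 | < 3.1 |

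The SAP categories are Normal, NCS and CS. The count below treats Grade 1 or above as equivalent to Abnormal. That is an assumption, since the central laboratory's reference ranges are not in the documents.

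**Two-direction analyte (potassium).** Signed grades run from −4 to +4, which is 9 levels.

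- Graded table: 9 × 9 = 81 cells. SAP table: 3 × 3 = 9 cells.
- Abnormal to abnormal: 8 × 8 = 64 graded cells, against 2 × 2 = 4 in the SAP table.
- Of the 64: reversals between low and high, 2 × 4 × 4 = 32; same-direction worsening, 2 × 6 = 12; same-direction improvement, 12; unchanged, 8. Sum: 32 + 12 + 12 + 8 = 64.

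All 32 reversals lose their direction whatever labels are given. The 12 worsenings are visible only if the label moves from NCS to CS.

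**One-direction analyte with four numeric grades (ALT).** 5 × 5 = 25 cells, of which 4 × 4 = 16 are abnormal to abnormal: 6 worsenings, 6 improvements and 4 unchanged.

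These are counts of table cells, not of subjects or probabilities.

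**Examples with both values labelled NCS:**

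| Potassium, baseline to later | Appendix II | SAP shift table |
|---|---|---|
| 5.1 to 5.5 | Grade 1 high to Grade 3 high | NCS to NCS, no shift |
| 3.5 to 5.2 | Grade 1 low to Grade 1 high | NCS to NCS, no shift |

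**Do the other outputs recover these?**

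- Adverse events: laboratory values enter through the CS label, so a result left as NCS is not carried into the graded tables by that route.
- Continuous summaries: a rise from 5.1 to 5.5 (+0.4) in one subject and a fall from 5.5 to 5.1 (−0.4) in another give a mean change of zero. Minimum and maximum show one extreme subject per visit and arm, not how many crossed a limit.
- Listings: they hold every value but do not compare arms.

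**The case against.** The best counter-argument is that serious deteriorations are covered elsewhere. A reader might infer that potassium going from 3.3 to 5.7 mEq/L (Grade 2 low to Grade 4 high), or ALT from 3 to 12 × ULN (Grade 2 to Grade 4), would vanish as CS to CS. The documents do not support that. The SAP's rule that CS abnormalities become adverse events is not limited to new findings. Those events are tabulated by grade, and preferred terms can carry direction. Protocol section 10 also counts clinically significant laboratory changes and unexpected worsening of pre-existing conditions as adverse events. The potassium swing of 5.7 − 3.3 = 2.4 would also set the arm's maximum change unless another subject's was larger. This part of the objection stands.

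A reader might also infer that the shift tables cannot show worsening at all, or that the SAP contradicts the protocol. Neither holds. Normal to NCS, Normal to CS and NCS to CS are all visible. Appendix II is headed as grading for adverse events, describes its laboratory limits as guidance that depends on local normal ranges, and was adapted from a healthy-volunteer vaccine scale. Neither document promises to grade every laboratory value, and Protocol 8.4.3 makes the safety analysis descriptive.

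Finally, not every Appendix II grade can be derived from a laboratory result. Grade 4 for BUN and for high glucose, and all urine Grade 4s, are clinical events. Urine blood is graded by microscopy, which Protocol 5.9 does not list. Hemoglobin has both an absolute and a change-from-baseline scale, and bilirubin has two rows depending on the liver tests. This limits the remedy but does not remove the gap for NCS results.

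**Conclusion.** The point holds as a modest reporting weakness. The shift tables lose worsening within a category, notably NCS to NCS, and they lose low/high direction. Values called CS should surface as graded adverse events. Results left as NCS are compared between arms only through means, medians, SDs and single extremes, with no graded or directional count.

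The loss of direction matters against Appendix II for four collected analytes: sodium, potassium, glucose and white cells. The loss of severity levels applies to every numerically graded test. How many subjects would be affected cannot be estimated, because the documents give neither the frequency of abnormal baselines nor how investigators will apply the CS label. No primary or secondary efficacy result depends on this. The stopping rule in Protocol 11.1 uses graded, treatment-related adverse events, not the shift tables.

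**What to change.** In SAP 5.2 and Tables 14.3.2.2, 14.3.3.2 and 14.3.4.2, add by arm a shift from baseline to worst post-baseline value:

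- by Low/Normal/High; and
- where Appendix II gives numeric limits, by Appendix II grade, with low and high directions in separate tables.

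Keep the CS/NCS table as a supplement. State these derivation rules:

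- Grade only as far as the limits are numeric; for example, BUN and high glucose stop at Grade 3.
- Use the absolute hemoglobin scale for the shift, and report the change-from-baseline hemoglobin grade separately.
- Say which bilirubin row applies, according to the concurrent liver tests.
- Keep CS/NCS for chloride, HDL, LDL, hematocrit and any urine item that cannot be graded from the result collected.

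The cost is SAP wording, these rules and modest programming. The central laboratory already supplies the values, so no new data are needed. The drawback is many low-grade entries, because the scale derives from one for healthy volunteers.
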